# 11.7 Statistical Analysis of Exploratory Objective 1.3.2 Growth Factor and Cytokine Responses

Objective: Measure growth factor and cytokine responses in children and young adults with recurrent ependymoma after treatment with a second course of irradiation, and explore associations between these and other measures of CNS effects and clinical and treatment factors.

Growth factor and cytokine responses in serum will be measured longitudinally before, during and post radiation therapy in consenting patients. Hence the planned exploratory analyses based on this data will mainly utilize longitudinal models. We will study possible associations between cytokine levels and demographic and clinical variables, response to treatment as measured by PFS as well as between cytokine levels and various side effects. We will investigate possible associations between the change in cytokine levels and factors such as radiation dose and irradiated volume, tumor volume, tumor response, surgical and host factors, etc. We will also evaluate presence of associations between cytokine responses and measures of sleep, fatigue and function as well as associations between cytokine responses and neurological, endocrine and cognitive/quality of life parameters. Additionally, we will examine whether an association exists between dose distribution and cytokine response. Considering the large number of exploratory analyses planned for these data, the multiplicity issues that will arise will be addressed by reporting false discovery rate estimates.

## 11.8 Statistical Analysis of Exploratory Objective 1.3.3 Radiogenomics

Objective: Conduct a variety of exploratory genetic analyses on tumor samples (and blood where a germline control is required), including but not limited to

St. Jude Children's Research Hospital IRB NUMBER: Pro00004349

IRB APPROVAL DATE: 02/01/2023

broad (genome-wide/array based) or focused (gene-specific) analyses at the DNA, RNA, or protein level and next generation sequencing in an effort to better understand the biology of ependymoma. Explore associations between molecular findings and treatment response and various side effects including vasculopathy, hearing loss, cognitive deficits, and growth hormone deficiency and other measures as appropriate.

This objective carries a general goal of exploring the genetic basis of ependymoma in an effort to identify genetic variations which may associate with tumor formation, treatment responses and toxicity. We will use statistical association tests, as appropriate, to investigate the association between genotypes and these phenotypes of interest. We will compare sequence/genetic variations from germline, untreated tumor and treated tumor samples to pinpoint the genetic events occurring during tumor initiation and development. Considering the large number of exploratory analyses planned for these data, the multiplicity issues that will arise will be addressed by reporting false discovery rate estimates.

A important goal of this analysis is to identify genetic variations in germline that predict for side effects from RT with the long-term aim of screening susceptible patients prior to irradiation and to study the biology of late effect. We will investigate genetic variants associated with side effects related phenotypes: vasculopathy, hearing loss, cognitive deficiencies, and hormone deficiencies by genome-wide association studies and candidate gene analyses. The currently known candidate genes and gene mutations for the phenotypes of interest are described below. However, since these data won't be available for several years from the initiation of enrollment and in some cases later if longer term follow-up is needed, the list of candidate genes may change substantially by the time we are ready to perform these analyses. Hence, the analysis plan below merely reflects the current state of knowledge and is subject to change.

Genetic Abnormalities Associated with Vasculopathy: The candidate genes based on current knowledge include: 1) gene HgS, IL4R, TNF, ADRB, VCAM-1 and LDLR which were associated with stroke risk in sickle cell disease (SCD) patients; 2) gene Factor II, Factor V, MTHFR and PAI-1 and promoter region of GPx-3 gene which were associated with venous sinus thrombosis and arterial ischemic stroke; 3) gene ELNINT20/INT23, COL1A2 and TNFRSF13B which were associated with intracranial aneurysm (IA) risk; 4) inositol 1,4,5-triphosphate 3-kinase C (ITPKC) gene which were associated with Kawasaki disease susceptibility and formation of coronary artery aneurisms; 5) HLA-AW24, -BW46, and -BW54 serotypes which are associated with Moya-moya syndrome, defined as bilateral severe stenosis or occlusion of the internal carotid arteries with collateral formation.

Genetic Abnormalities Associated with Hearing Loss: The candidate gene mutations under our investigation include: 1) mutations of the GJB2 gene which was associated with recessive and sporadic deafness; 2) mutations in the

St. Jude Children's Research Hospital IRB NUMBER: Pro00004349

IRB APPROVAL DATE: 02/01/2023

Rev. 3.2 dated: 1/19/2023 Protocol document date: 1/19/2023 IRB Approval date:

mitochondrial 12S ribosomal RNA gene which were associated with ototoxicity for patients taken Aminoglycoside antibiotics; 3) GSTP1 gene and megalin mutations which were associated with cisplatin-induced ototoxicity.

Genetic Abnormalities Associated with Cognitive Deficiencies: The candidate genes under our investigation include: 1) GDI1, oligophrenin, PAK3, FMR2, IL1RAPL, TM4SF2, VCX-A, ARHGEF6, GPC3, GPC4 and HTR2A which were associated with nonsyndromic mental retardation (NSMR); 2) SNAP-25 gene and APOE gene which were associated with cognitive function; 3) 894TT genotype of NOS3 gene which was associated with cognitive decline following radiation therapy; 4) COMT genotype which was associated with white matter performance and resiliency against late effects of irradiation.

Genetic Abnormalities Associated with Hormone Deficiencies: The candidate genes under our investigation include: genetic aberrations in GST (GSTM1, GSTP1, GSTT1) which have been associated with the risk of relapse of certain cancers and modulate response to therapy; GSTM1 gene was associated with susceptibility to growth hormone deficiency.

# 11.9 Statistical Analyses of Exploratory Objective 1.3.4: Association of prior chemotherapy with PFS and OS distributions.

Cox proportional hazard models will be used to explore possible association of chemotherapy given prior to re-irradiation with outcome. Due to the expected limited sample sizes for any chemotherapy agent, the results of these exploratory analyses will be considered as descriptive.

11.10 Statistical Analyses of Exploratory Objective 1.3.5: To compare the progression-free and overall survival distributions for children (age > 3 years) and young adults with recurrent ependymoma and 1q gain treated with a second course of irradiation (focal or craniospinal) while monitoring for excessive central nervous system necrosis.

Of the 117 patients in RT1 cohort, total of 20 had a "distant or combined" pattern of failure, 8 did and 12 did not have 1q gain. Total of 22 patients had a "local" pattern of failure, 4 did and 18 did not have 1q gain. A total of 75 patients did not experience treatment failure (tumor progression), 4 did and 71 did not have 1q gain. The detailed frequency is shown in Table 1. There is association between type of failure with 1q gain status (p=0.0003, Chi-square test).

Table 1. Pattern of failure by 1q gain status

Pattern of Failure		1q gain									
	No	No Yes									
Distant or Combined	12	8	20								
Local Only	18	4	22								
None	71	4	75								

St. Jude Children's Research Hospital

IRB NUMBER: Pro00004349
IRB APPROVAL DATE: 02/01/2023

Rev. 3.2 dated: 1/19/2023

Total	101	16	117
1 1 0 ta 1	101	10	11/

Cumulative incidence of Distant or combined failure by 1q gain status The cumulative incidence of distant or combined failure analysis with competing risks was assessed. The distant or combined failure was considered as event and other events (local failure and death) were considered as competing risks. Patients with no events were considered as censored. The cumulative incidence with competing risks is shown in Table 2 and plotted in Figure 1. The cumulative incidence of distant or combined failure after 14 years of follow-up was  $0.1256 \pm 0.0346$  (Table 2) for patients without 1q gain, considering the competing risk factors. The cumulative incidence of distant or combined failure after 12 years of follow-up was  $0.5000 \pm 0.1328$  for patients with 1q gain, considering the competing risk factors. The Chi-square test had P value of <0.0001 (Table 2), indicating that there was statistically significant difference for the cumulative incidence of distant or combined failure among patients with the presence of 1q gain vs. absence of 1q gain.

Table 2. Cumulative incidence of distant or combined failure for infratentorial ependymoma patients with competing risks Chi-square = 15.8814, df = 1, p = 0.0000674383

attents wit		-		no_Gain_1q							Gain_1q							
Years since start of RT	Risk	Fail	Fail other	Cens	CI	SE	Years since start of RT	Risk	Fail	Fail other	Cens	CI	SE					
0	101	0	0	0	0.0000	0.0000	0	16	0	0	0	0.0000	0.0000					
1	101	3	3	0	0.0297	0.0170	1	16	4	1	0	0.2500	0.1123					
2	95	3	6	0	0.0594	0.0236	2	11	2	2	0	0.3750	0.1267					
3	86	4	7	2	0.0991	0.0299	3	7	2	0	0	0.5000	0.1328					
4	73	0	2	2	0.0991	0.0299	4	5	0	0	0	0.5000	0.1328					
5	69	0	0	8	0.0991	0.0299	5	5	0	0	1	0.5000	0.1328					
6	61	1	1	4	0.1114	0.0320	6	4	0	0	1	0.5000	0.1328					
7	55	1	1	8	0.1259	0.0346	7	3	0	1	0	0.5000	0.1328					
8	45	0	0	7	0.1259	0.0346	8	2	0	0	0	0.5000	0.1328					
9	38	0	2	6	0.1259	0.0346	9	2	0	0	0	0.5000	0.1328					
10	30	0	1	5	0.1259	0.0346	10	2	0	0	1	0.5000	0.1328					
11	24	0	0	11	0.1259	0.0346	11	1	0	0	0	0.5000	0.1328					
12	13	0	0	6	0.1259	0.0346	12	1	0	0	1	0.5000	0.1328					
13	7	0	0	6	0.1259	0.0346												
14	1	0	0	1	0.1259	0.0346												

Rev. 3.2 dated: 1/19/2023 Protocol document date: 1/19/2023 IRB Approval date:

[figure not shown]

Figure 1: Cumulative Incidence of Distant or Combined Failure for RT1 Patients with Competing Risks

So, the 1q gain status is important factor to consider when plan treatment of cranial spinal irradiation vs. focal irradiation by historic data. We will offer patients the optional second course of cranial spinal irradiation treatment when they have 1q gain in this procol. We will compare PFS and OS of patients with 1q gain status who receive cranial spinal irradiation vs. focal irradiation by log rank test if sample size is reasonable big. Due to the expected limited sample sizes, the results of these exploratory analyses will be considered as descriptive.

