#### **Protocol Summary**

Protocol MNEMONIC and Title: RERTEP - A Phase II Trial of Surgery and

Fractionated Re-irradiation for Recurrent Ependymoma

Principal Investigator: [name], DO, PhD

**IND Holder:** C-methionine, IND 104987, Sponsor of IND: St. Jude Children's Research Hospital

**Brief Overview:** There is a need to determine the role of re-irradiation in patients with recurrent ependymoma after prior therapy that includes fractionated radiation therapy administered with curative intent. Outcomes reported from St. Jude Children's Research Hospital suggest that a proportion of children with recurrent ependymoma after prior irradiation may be successfully treated with additional surgery and a second course of irradiation; however, there are a number of unanswered questions about this approach including portability, morbidity and mortality, and the biological basis for success. Responding to these questions requires prospective study of outcomes and tumor biology.

Intervention: Neurosurgery and fractionated irradiation.

Rev. 3.2 dated: 1/19/2023

Protocol document date: 1/19/2023

Brief Outline of Treatment Plan: The goal of this study is to determine the feasibility and safety of treating recurrent ependymoma with a second course of irradiation using cumulative doses that exceed those used in routine clinical practice. Surgery is an important part of this study and will be used to document recurrent ependymoma and reduce the tumor burden when feasible. Patients with local failure after prior surgery and focal irradiation will undergo surgery and focal re-irradiation; however, those age > 3 years with tumors having 1q gain will be offered craniospinal irradiation. Those with metastatic disease limited to the neuraxis will receive craniospinal irradiation after surgery. Patients with combined local and distant failure will be treated with surgery and craniospinal irradiation. Patients will be stratified for outcome according to diagnosis and prior therapy. All patients will be evaluated for the effects of the treatment regimen.

St. Jude Children's Research Hospital IRB NUMBER: Pro00004349 IRB APPROVAL DATE: 02/01/2023

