#### 4.3 **Stratification for Treatment**

Stratification for treatment of ependymoma will be determined when radiation therapy planning is initiated. There is no limit to the number of participants in each stratum.

Stratum 1 (initial pattern of failure is local); disease confined to primary site; age >12 months at time of enrollment to < 21 years. Treatment: focal irradiation.

Stratum 2 (initial pattern of failure is metastatic); neuraxis metastatic disease without equivocal evidence of local failure; age > 36 months at time of enrollment to < 21 years. Treatment: craniospinal irradiation.

Stratum 3 (initial pattern of failure is both local and metastatic): neuraxis metastatic disease with unequivocal evidence of local failure; age > 36 months at time of enrollment to < 21 years. Treatment: craniospinal irradiation.

Stratum 4 (initial pattern of failure is local): disease confined to primary site; age >36 months at time of enrollment to < 21 years; tumor shows presence of 1q gain. Treatment: craniospinal irradiation (optional).

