#### 5.7.1 Targeting for patients with local recurrence

**Primary Site Irradiation** 

The patient with recurrent disease at the primary site and no evidence of metastasis will receive focal irradiation of the primary site using the targeting guidelines provided below. Exceptions will include patients with tumors demonstrating the presence of 1q gain at any point in their treatment history. They will be given the option of craniospinal irradiation and will follow targeting guidelines similar to those who have metastatic disease.

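### The 1q-gain comparison of craniospinal with focal irradiation is not limited to local failure, so as written it confounds treated volume with disease extent

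*Combined protocol and SAP*

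**What the plan says.** Objective 1.3.5, repeated in the title of section 11.10, covers "children (age > 3 years) and young adults with recurrent ependymoma and 1q gain treated with a second course of irradiation (focal or craniospinal"). Failure pattern is not mentioned. The analysis sentence in 11.10 reads "We will compare PFS and OS of patients with 1q gain status who receive cranial spinal irradiation vs. focal irradiation by log rank test". It is conditional on a sufficient sample size, and the results are declared exploratory and descriptive because numbers will be small. No stratification or adjustment is planned.

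The treatment rules are in three places:

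- **Protocol Summary.** On metastatic disease: "Those with metastatic disease limited to the neuraxis will receive craniospinal irradiation after surgery". On combined failure: "Patients with combined local and distant failure will be treated with surgery and craniospinal irradiation". Neither depends on 1q status.
- **Section 4.3.** Stratum 2 (metastatic) and Stratum 3 ("neuraxis metastatic disease with unequivocal evidence of local failure") are assigned craniospinal irradiation. Stratum 4 is disease confined to the primary site, age over 36 months and 1q gain: "Treatment: craniospinal irradiation (optional").
- **Section 5.7.1.** On local recurrence with 1q gain: "They will be given the option of craniospinal irradiation and will follow targeting guidelines similar to those who have metastatic disease".

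Section 11.2, on neurological, endocrine and cognitive outcomes, recognises that focal and craniospinal treatment are not allocated at random and calls for adjustment. Section 11.10 has no such statement.

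**The concern.** A choice of volume exists only for local failure with 1q gain. Under the written definition, patients with metastatic or combined failure and 1q gain also count in the craniospinal arm, and none of them can appear in the focal arm. Disease extent then largely determines the arm, and an unadjusted log-rank test cannot separate the effect of volume from that of extent.

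This is the only planned comparison that bears on the optional craniospinal treatment in Stratum 4. A curve of mostly metastatic relapse set against purely local relapse could be read as evidence about that option, in either direction, when it largely reflects case mix.

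**Working it through.** **1. The plan's own figure.** The 11.10 table of failure pattern by 1q gain (no, yes) is: distant or combined 12, 8; local 18, 4; none 71, 4. The Pearson chi-square is 16.54 on 2 df, p = 0.000256, which agrees with the stated 0.0003. Among failures alone, 8/20 against 4/22 gives Fisher p = 0.17, so the split by pattern is imprecise and serves here only as a proxy.

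**2. Make-up of the craniospinal arm as written.** Let f be the share of local 1q-gain patients who choose craniospinal treatment (an assumption; the documents give no figure). With 8 distant or combined and 4 local patients, the metastatic or combined share is 8/(8 + 4f):

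- f = 0.25: 8/9 = 89%
- f = 0.50: 8/10 = 80%
- f = 0.75: 8/11 = 73%

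The focal arm is 100% local at every f.

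**3. Sensitivity to the mix.** The historical retreatment cohort (Table 11.0) was 29/50 = 58% local and 21/50 = 42% distant or combined. Applying the RT1 pattern-specific 1q rates gives 0.42 × 8/20 = 0.168 and 0.58 × 4/22 = 0.105. At f = 0.5 the share is 0.168/(0.168 + 0.053) = 76%. If 1q gain were unrelated to pattern, it would be 0.42/(0.42 + 0.29) = 59%.

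**4. Expected numbers.** RT1 proportions applied to 90 patients:

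- 1q gain: 90 × 12/42 = 25.7
- distant or combined with 1q gain: 90 × 8/42 = 17.1
- local with 1q gain: 90 × 4/42 = 8.6

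The step 3 mix gives 90 × 0.168 = 15.1 and 90 × 0.105 = 9.5.

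**5. What case mix alone could do.** The historical estimates come from the section 11.0 tables by failure pattern and retreatment. The metastatic or combined mix M uses the historical 16:5 split of distant to combined failures. At f = 0.5 the craniospinal arm is 0.8M + 0.2 × (local value), which assumes that volume has no effect.

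| | Local/focal (n=22) | Distant/CSI (n=16) | Combined/CSI (n=5) | M | CSI arm | Gap from focal |
|---|---|---|---|---|---|---|
| 3-year PFS | 0.605 | 0.587 | 0.250 | 0.507 | 0.526 | −0.079 |
| 5-year PFS | 0.432 | 0.503 | 0.250 | 0.443 | 0.441 | +0.009 |
| 3-year OS | 0.781 | 0.802 | 0.250 | 0.671 | 0.693 | −0.088 |
| 5-year OS | 0.533 | 0.802 | 0.250 | 0.671 | 0.643 | +0.110 |

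On 3-year PFS the apparent hazard ratio is ln 0.526 / ln 0.605 = 1.28. With a craniospinal arm made up only of distant failures it is 1.06; with only combined failures it is 2.76. The sign of the gap changes with endpoint and time. The tables are not split by 1q status, volume and pattern are inseparable in them, and the combined group has 5 patients. The three-group log-rank p was 0.2416 for PFS and 0.0242 for OS.

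**6. After restriction to local failure.** About 9 patients remain. At the design's expected failure proportion (67/90) that is 9 × 67/90 = 6.7 events. By the Schoenfeld formula with a 1:1 split and two-sided 5%, power for a hazard ratio of 0.5 is Φ(√(6.7 × 0.25) × 0.693 − 1.96) = 14%. Reaching 80% power would take 66 events.

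**The case against.** **The context points to Stratum 4.** The sentence before the comparison describes the optional craniospinal offer, which exists only for local failure with 1q gain, and the objective's age limit matches that offer. A reader could fairly take the comparison to cover only patients who had the choice. This may well be the intent, but neither 1.3.5 nor 11.10 says so, and an unstated set can be settled after results are seen. The age limit changes nothing here, since section 3.2 already excludes metastatic patients under 3.

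**The analysis is exploratory and descriptive.** No stopping rule, confirmatory claim or treatment assignment depends on it. That lowers the stakes and stands as a limit on severity. It is not an answer to confounding: the reason the plan gives is small numbers.

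**The direction of bias is uncertain.** A reader might infer that the comparison is bound to make craniospinal irradiation look harmful or useless. The documents do not support this. Distant and local failures had nearly equal 3-year PFS, and distant failures treated craniospinally had higher 5-year OS.

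**The size rests on proxies.** The RT1 figures come from 12 first failures, in a cohort that Table 2 of 11.10 labels infratentorial. The trial takes all intracranial ependymoma and allows several progressions. This stands, so ranges are given.

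**Restriction does not make the comparison causal.** Families and physicians still choose the volume. This also stands.

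**Conclusion.** The point holds as one of definition and confounding. Under the written set, extent of disease and volume are nearly the same variable. Metastatic or combined patients would form about 73% to 89% of the craniospinal arm for uptake of 75% to 25% at RT1 proportions, and about 76% at half uptake with the historical retreatment mix. The focal arm contains none. The figures assume that the RT1 1q rates apply to this trial.

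Two stronger readings should be resisted. The documents do not show which direction the bias would take. Nor would a restricted analysis establish whether volume matters: it removes confounding by extent but not self-selection, and rests on about 9 patients. The change is worth making because it costs little, but the analysis stays descriptive.

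**What to change.** In objective 1.3.5 and section 11.10:

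1. Define the comparison set as patients who meet the Stratum 4 definition (disease confined to the primary site, age over 36 months at enrolment, 1q gain), whichever volume they received.
2. Compare by volume received, giving PFS and OS estimates with confidence intervals.
3. Report Strata 2 and 3 patients with 1q gain separately.
4. Tabulate prognostic factors by volume: for example, duration of initial disease control, histology at recurrence and extent of resection, which section 11.0 links to outcome.

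The cost is a wording change to one exploratory objective and its analysis section. Treatment, sample size and data collection do not change. The downside is that the set falls from about 26 patients to about 9, so intervals will be wide, and the text should say that volume was not randomly allocated.

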# 11.11 Monitoring Outcomes for the Retrospective Cohort

The primary objective of this study is to estimate the distributions of PFS and OS after re-irradiation for patients with ependymoma and comparing them to retrospective historical data. Because of the clinicopathologic factors that predict for disease control and functional outcomes and clinical and treatment factors associated with complications evolve over time and will affect the analyses performed for patients enrolled on this study, we will periodically update outcomes from our retrospective cohort to be published and used for comparative analysis. This means that RERTEP will include a retrospective assessment of

St. Jude Children's Research Hospital IRB NUMBER: Pro00004349 IRB APPROVAL DATE: 02/01/2023

disease control and functional outcomes for re-irradiated ependymoma patients treated prior to the activation of this study or those not enrolled. The retrospective review will include an update of the PFS and OS analyses used to develop the statistical design for this study, limited functional outcome and complication assessments used to design the secondary and exploratory aims, incorporate and updating clinicopathologic assessments routinely performed for patients with ependymoma, and other clinical and treatment factors and measures of CNS effects. The list of patients to whom this retrospective research applies will be available through protocol documents in TRACKS.

